4. ANALYSIS POPULATIONS

Population	Definition / Criteria	Analyses Evaluated
Screened	
 All participants who were screened for eligibility 	
 Study Population
Enrolled	
 All participants who passed screening and entered the study. Note screening failures (who never passed screening even if rescreened) and participants screened but never enrolled into the study (Reserve, Not Used) are excluded from the Enrolled population as they did not enter the study. 	
 Study Population
Randomized	
 All participants who were randomly assigned to treatment in the study. This population will be based on the treatment the participant was randomized to. 	
 Study Population
Safety	
 All randomized participants who received at least one dose of study treatment. This population will be analysed based on the treatment the participant actually received. 	
 Study Population Safety
Intent-To-Treat Exposed (ITT)	
 All randomized participants who meet the study criteria and are enrolled into the study with documented evidence of having received at least one dose of treatment and at least one post-baseline HIV-1 RNA measurement. This will be the primary population for the final efficacy analysis for all active treatment groups. This population will be based on the treatment the participant was randomized to. 	
 Efficacy
Per-Protocol (PP)	
 all participants who meet study criteria and are enrolled into the study with documented evidence of having received all doses and all post-baseline HIV-1 RNA measurement. Protocol deviations that would exclude participants from the PP population are defined in Section 4.1 (Protocol Deviations) and Appendix 1: Protocol Deviation Management and Definitions for Per Protocol Population. The PP set will not be analysed if no participants drop out of ITT population. 	
 Efficacy

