10.1.3. Population of Interest

The primary pharmacodynamics analyses will be based on the PP population, unless otherwise specified.

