10.1.4.1. Statistical Methodology Specification**Model Specification**

- To model the dose-response relationship, a frequentist simplified Emax model is planned. This model assumes the following form:

$$\Delta VL = \frac{(Emax)}{1 + \left(\frac{ED50}{Dose}\right)} + \epsilon$$

Where:

- ΔVL is the change from baseline, defined as Log10 Maximum change from baseline to Day 8 and change from baseline to Day 8 (both parts) in plasma HIV-1 RNA on log10 scale.
- Emax is the maximum response
- ED50 is the dose that attains the 50% of the maximal effect ϵ is a random error assumed to be normally distributed with mean zero and constant variance (σ^2)

The observed maximum change from baseline in Plasma HIV-1 RNA will be used as the response variable in the Emax model.

- The derived data from this Emax model (estimates Emax, ED50 and Variance along with their standard error, and 95% CI) will be tabulated and a dose-response curve will also be produced.
- If problems are encountered Emax model or if the Emax shape is a poor fit for the data and a linear relationship looks plausible across the dose range, then a linear model will be considered of the form:

$$\Delta VL = \alpha * Dose + \epsilon$$

Model Checking & Diagnostics

- Model assumptions will be applied, but appropriate adjustments may be made based on the data.

Model Results Presentation

- The statistical model will use doses from both parts for model fitting.
- The derived data from this Emax model (estimates Emax, ED50 and Variance along with their standard error, and 95% CI) will be tabulated and an exposure-response curve will also be produced.

Example SAS Code:

```
PROC NLMIXED;
PARMS E0 = EST EMAX = EST ED50 = EST S2E = SE;
BOUNDS E0>0 EMAX>0 ED50>0 S2E>0;
PRED = E0 +(EMAX-E0)/(1+(ED50/DOSE));
MODEL RESPONSE ~ NORMAL (PRED, S2E);
PREDICT PRED OUT=DOSE;
RUN;
```

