13. APPENDICES

13.1. Appendix 1: Protocol Deviation Management and Definitions for Per Protocol Population

13.1.1. Exclusions from Per Protocol Population

A participant meeting any of the following criteria will be excluded from the Per Protocol population:

Number	Exclusion Description
1	Participant who deviated from any inclusion/exclusion criteria
2	Participant who did not receive correct treatment which the participant was randomized to
3	Participant who have missed at least one dose of GSK3640254
4	Participant who did not have Visit 6 HIV-RNA measurement
5	Not withdrawn after meeting the following stopping criteria 
 • Liver chemistry stopping criteria • QTc stopping criteria • Stopping criteria based on Laboratory Abnormality and Adverse Event
6	Informed Consent 
 • Study-specific assessments conducted prior to obtaining proper consent.
7	Study visits performed out of window 
 • Consecutive participant study visits performed out of window • Multiple study visits performed out of window by various Participants (Trending)
8	Incorrect study treatment 
 • Unresolved IP accountability discrepancy • IP storage guidelines not followed • IP incorrectly administered • IP accountability not done
9	Lack of PI oversight
10	Participant Used prohibited medication
11	Participant became pregnant while on study
12	Safety assessments not performed when clinically relevant 
 • Central safety lab samples not collected and/or not properly sent to Q2 when clinically relevant

CONFIDENTIAL

208132

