13.11.11. Pharmacodynamic Tables

Pharmacodynamic: Tables					
No.	Population	IDSL / Example Shell	Title	Programming Notes	Deliverable [Priority]
PD Linear and Emax Models					
5.1.	PP	PD_T1	Summary of Estimates from Dose-Response Model	Only include visits from Day 1 to Day 8 for the HIV-RNA change. Part 1 and Part 2 doses all included in the statistical mode.	SAC

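### The SAP's dose-response equation and its example code are different models, neither defined at Dose = 0, and the Per-Protocol set named for the fit does not exclude placebo

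*SAP*

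**What the plan says.** SAP 10.1.4.1 opens with "To model the dose-response relationship, a frequentist simplified Emax model is planned". The displayed equation is Emax/(1 + ED50/Dose) plus a normal error. It has no baseline term, and the estimates to be tabulated are Emax, ED50 and the variance (also SAP 10.1.2). The example code below it declares "PARMS E0 = EST EMAX = EST ED50 = EST S2E = SE", bounds E0 above zero, and computes "PRED = E0 +(EMAX-E0)/(1+(ED50/DOSE".

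On who is analysed, SAP 10.1.3 states "The primary pharmacodynamics analyses will be based on the PP population, unless otherwise specified". SAP Section 4 defines that set as "all participants who meet study criteria and are enrolled into the study with documented evidence of having received all doses"; complete viral load data after baseline are also required. It is not restricted to active arms. Of the exclusions in SAP 13.1.1, the nearest to placebo is "Participant who have missed at least one dose of GSK3640254", which does not remove placebo participants as a group. SAP 2.3 plans 2 placebo participants in each part.

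On what is pooled, the note to Table 5.1 (SAP 13.11.11) reads "Part 1 and Part 2 doses all included in the statistical mode". SAP 10.1 selects between the Emax and linear models by lowest AIC. The linear form in 10.1.4.1 is alpha*Dose.

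**The concern.** The model cannot be evaluated for part of the population named for it, and the plan does not say what happens to those records. How much this matters depends on which model is run, and the SAP leaves that open because its equation and code differ. If the code is followed, E0 is the response at zero dose, and placebo is the only group that observes it directly. Without placebo, E0 must be extrapolated from the active doses and trades off against ED50, one of the quantities Table 5.1 is there to report.

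There is a second consequence. The linear alternative is defined at zero, so placebo could remain in that fit and be absent from the Emax fit. The AIC values would then come from different data.

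**Working it through.** **Number of records.** Five active cohorts of 6 plus two placebo cohorts of 2 give 5 × 6 + 2 × 2 = 34 (14 in Part 1, 20 in Part 2). This reproduces the planned total in protocol 5.2. Up to 4 records have Dose = 0 and 30 have Dose > 0.

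**Behaviour at zero.** Both SAP expressions contain ED50/Dose, a division by zero when Dose = 0. Multiplying numerator and denominator by Dose gives Emax*Dose/(ED50 + Dose), which is identical for Dose > 0 and equals 0 at Dose = 0. The code form becomes E0 + (Emax − E0)*Dose/(ED50 + Dose), which equals E0 at Dose = 0.

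**Inputs for the size.**
- Doses 10, 40, 80, 140 and 200 mg, 6 participants each, with or without 4 at zero (SAP 2.3).
- SD 0.4 log10 (protocol 10.1.1).
- Emax 1.8 log10, assumed. With E0 = 0, 1.5 and 2.0 give the same ratios, because Emax and SD cancel from them.
- ED50 is varied. For a simple Emax curve with p percent of maximum at dose d, ED50 = d(100 − p)/p. Protocol Table 1 gives 10 × 52.4/47.6 = 11.0 mg at 10 mg and 200 × 5.4/94.6 = 11.4 mg at 200 mg, so about 11 mg. The SAP 2.3 schematic labels 40, 80 and 140 mg as 30%, 75% and 90% of maximum, which imply 40 × 70/30 = 93, 80 × 25/75 = 27 and 140 × 10/90 = 16 mg. A range is therefore needed.

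**Formula.** With x = Dose/(ED50 + Dose), the derivatives of the code-form mean are 1 − x for E0, x for Emax and −(Emax − E0)*Dose/(ED50 + Dose)² for ED50. The written form has only the last two, with E0 = 0. The large-sample SE of ED50 is SD times the square root of the ED50 diagonal element of (J'J)⁻¹, where J stacks these derivatives over participants.

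**Written equation.** At Dose = 0 both derivatives are zero, so placebo adds nothing to J'J. At ED50 = 11 the SE is 4.56 mg with or without placebo. In 200 simulated trials at each of six settings (ED50 11, 20 or 40 mg; E0 0 or 0.2), the fitted ED50 differed by less than 0.005 mg, which is optimiser tolerance. Only the residual variance is affected.

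**Code form (E0 = 0, Emax 1.8).**

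| True ED50 (mg) | SE without placebo | SE with placebo | Ratio |
|---|---|---|---|
| 11 | 23.3 | 5.2 | 4.5 |
| 20 | 25.9 | 10.4 | 2.5 |
| 40 | 39.9 | 24.5 | 1.6 |
| 93 | 107 | 81 | 1.3 |

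**AIC.** AIC is built on the log-likelihood summed over the records fitted. A value from 30 records and one from 34 differ partly because the data differ, so choosing the lower does not compare the models.

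**The case against.** The strongest reply is that the specified model is the written one. It has no E0, SAP 10.1.2 reports none, and under it placebo is irrelevant to ED50. The E0 line sits in a block labelled as example code and closely matches the code in SAP 11.1.3, where E0 does belong to the stated model. This stands, and it limits the harm to the code form. It also confirms that text and code specify different analyses, which a programmer has to resolve without guidance.

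A second reply is that only active doses were meant, since Section 10 speaks of doses from both parts and never says that placebo enters the fit. That reading is coherent. But the SAP is explicit elsewhere: the PK/PD set requires the PK population, hence receipt of GSK3640254, and the QTcF plot in 11.2 assigns placebo a concentration of 0. Section 10 does neither, while naming a population that contains placebo. Either intention needs a stated rule.

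Third, no formal hypotheses are tested, the relationship is to be explored, and 10.1.4.1 allows adjustments and a linear fallback. This stands and sets the severity.

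A reader might go further and infer that the procedure will stop or silently drop the placebo records. The documents do not describe software behaviour, so only the undefined expression is established. A reader might also infer that ED50 loses its anchor whichever form is used, or that its upper range runs to several hundred milligrams. The first is untrue of the written equation. The second comes from the code form fitted without placebo, mainly with ED50 set at 11 mg, and its upper limit depends on the optimiser's bounds.

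**Conclusion.** Wrong as written; minor. The expression is undefined for up to 4 of about 34 planned participants in the population named for the fit, and equation and code are not the same model. Under the written equation the cost is confined to the residual variance. Under the code, losing placebo inflates the SE of ED50 between about 1.3-fold (ED50 93 mg) and 4.5-fold (ED50 11 mg). These ratios rest on 6 participants per active dose, 4 on placebo, a common variance and a true Emax shape. The SEs in milligrams also rest on the assumed Emax of 1.8 log10 and the protocol's SD of 0.4. The 11 mg figure is a prediction made before Part 1, so the upper end of the inflation should not be read as the expected case. The AIC problem arises only if the two candidate models are fitted to different records, which the SAP does not rule out.

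**What to change.** Choose one model and write it identically in the text and the code of SAP 10.1.4.1, in the form defined at zero.

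- Preferred: E0 + (Emax − E0)*Dose/(ED50 + Dose), with E0 added to the estimates in 10.1.2 and Table 5.1. If placebo shows some drop, the form without E0 pulls ED50 down. In 200 simulated trials with E0 = 0.2, Emax 1.8 and true ED50 11 mg, the median ED50 was 8.35 mg without E0 and 10.79 mg with E0 and placebo included.
- Alternative: Emax*Dose/(ED50 + Dose), with E0 removed from the code.

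State that Part 1 and Part 2 placebo participants enter as Dose = 0. Require that the Emax and linear models be fitted to the same records before AIC is compared. The cost is a few lines of SAP text and code. For Dose > 0 the rewritten curves are identical to the present ones, and no extra data are needed.

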11. PHARMACOKINETIC / PHARMACODYNAMIC ANALYSES

11.1. PK/PD Analyses of HIV-1 RNA

11.1.1. Statistical Analyses / Methods

Scatter plots of plasma HIV-1 RNA change from baseline to Day 8 vs. plasma GSK3640254 PK parameters (AUC(0- τ), C_{max} and C _{τ}) will be generated separately for each active treatment. The Pearson's correlations between plasma HIV-1 RNA change from baseline to Day 8 and plasma GSK3640254 PK parameters will be summarized by treatment and overall.

Relationships between various PK parameters (AUC(0- τ), C_{max} and C _{τ}) and PD measures (Log₁₀ maximum change from baseline to Day 8 in plasma RNA and Log₁₀ change from baseline to Day 8 in plasma HIV-1 RNA) will be explored with various E_{max} models. Model selection will be based on Akaike Information Criteria (AIC) value, where model with the lowest AIC value will be considered the best model.

11.1.2. Population of Interest

The primary pharmacodynamics analyses will be based on the PK/PD population, unless otherwise specified. Part 1 Day 9~11 HIV RNA are excluded to fulfil the same dosing days and be used in one statistical model.

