10.1.1. Endpoint / Variables

- Log₁₀ Maximum change from baseline to Day 8 and change from baseline to Day 8 in plasma HIV-1 RNA

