10.1.4. Statistical Analyses / Methods

Details of the planned displays are provided in [Appendix 11](#): List of Data Displays and will be based on GSK Data Standards and statistical principles.

Unless otherwise specified, endpoints / variables defined in Section [10.1.1](#) will be summarised using descriptive statistics, graphically presented (where appropriate) and listed.

Descriptive Summary tables are separated for Part 1 and Part 2 while the summary table for statistical modelling results are combined for two Parts.

In endpoint descriptive summary tables, the maximum change from baseline includes all visits while in model fitting it only includes visits from baseline to Day 8 in HIV-1 RNA for both parts.

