13.3. Appendix 3: Assessment Windows**13.3.1. Definitions of Assessment Windows for Analyses**

Analyses will be presented by scheduled visits as collected in the CRF. The following table presents protocol defined assessment windows.

Part 1

Analysis Set / Domain	Parameter (if applicable)	Target	Analysis Window		Analysis Timepoint
			Beginning Timepoint	Ending Timepoint	
Safety and Efficacy	All	14 - 28 days prior to first dose	28 days prior to first dose	Day -1	Screen
Efficacy	HIV-1 RNA, HIV-1 genotype / phenotype	Day 1	Day 1	Day 1	Visit 1
		Day 2	Day 2	Day 2	Visit 2
		Day 3 or 4	Day 3	Day 4	Visit 3
		Day 5, 6, or 7	Day 5	Day 7	Visit 4
		Day 8, 9, or 10	Day 8	Day 10	Visit 5
		Day 11	Day 11	Day 11	Visit 6
		Day 12	Day 12	Day 12	Visit 7
		Day 13, 14, 15, 16, or 17	Day 13	Day 17	Visit 8
		Days 18 to final follow up visit day	Day 18	final follow up visit day	Follow-up
	CD4 and CD8	Day 1	Day 1	Day 1	Visit 1
Day 11		Day 11	Day 11	Visit 6	
Safety	Laboratory: Chemistry/ Haematology/ Urinalysis	Day 1	Day 1	Day 1	Visit 1
		Day 2	Day 2	Day 2	Visit 2
		Day 3 or 4	Day 3	Day 4	Visit 3
		Day 5, 6, or 7	Day 5	Day 7	Visit 4
		Day 8, 9, or 10	Day 8	Day 10	Visit 5
		Day 11	Day 11	Day 11	Visit 6
		Days 18 to final follow up visit day	Day 18	final follow up visit day	Follow-up
	Fasting Lipid Panel	Day 1	Day 1	Day 1	Visit 1
		Day 11	Day 11	Day 11	Visit 6
		Days 18 to final follow up visit day	Day 18	final follow up visit day	Follow-up
	ECG	Day 1 ¹	Day 1	Day 1	Visit 1
		Day 2 ²	Day 2	Day 2	Visit 2
		Day 3 or 4 ²	Day 3	Day 4	Visit 3
Day 8, 9, or 10 ³		Day 8	Day 10	Visit 5	
Days 18 to final follow up visit day ²		Day 18	final follow up visit day	Follow-up	

CONFIDENTIAL

208132

Analysis Set / Domain	Parameter (if applicable)	Target	Analysis Window		Analysis Timepoint
			Beginning Timepoint	Ending Timepoint	
	Vital Signs	Day 1	Day 1	Day 1	Visit 1
		Day 2	Day 2	Day 2	Visit 2
		Day 3 or 4	Day 3	Day 4	Visit 3
		Day 8, 9, or 10	Day 8	Day 10	Visit 5
		Days 18 to final follow up visit day	Day 18	final follow up visit day	Follow-up

NOTES:

¹ 12-lead ECG (triplicate reading, pre-dose; single readings at PK draws 2hr, 4hr, and 6hr)

² 12-lead ECG (single reading, pre-dose)

³ 12-lead ECG (single reading pre-dose and at PK draws 2hr, 4hr, and 6hr)

Part 2

Analysis Set / Domain	Parameter (if applicable)	Target	Analysis Window		Analysis Timepoint
			Beginning Timepoint	Ending Timepoint	
Safety and Efficacy	All	14 - 28 days prior to first dose	28 days prior to first dose	Day -1	Screen

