13.6.3. Efficacy

Efficacy Parameters
Plasma HIV-1 RNA

 • If there are two values within a time window, the latest value will be used for summaries and analyses
CD4+ T-cell

 • If there are two values within a time window, the average value will be used for summaries and analyses

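### The Day-8 cut in the pooled dose- and exposure-response models leaves Part 1 participants with a Day 9 or 10 Visit 5 without a Day-8 RNA, and ends their maximum change at Day 6 or 7

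*SAP*

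**What the plan says.** The dose-response model (SAP 10.1) and the exposure-response model (SAP 11.1) combine both parts. Each uses two responses, listed for the dose-response model in SAP 10.1.1 as "Maximum change from baseline to Day 8 and change from baseline to Day 8 in plasma HIV-1 RNA". SAP 10.1.4 keeps all visits in the descriptive tables, "while in model fitting it only includes visits from baseline to Day 8 in HIV-1 RNA for both parts". SAP 11.1.2 gives the reason: "Part 1 Day 9~11 HIV RNA are excluded to fulfil the same dosing days and be used in one statistical model". SAP 10.1.4.1 adds that "The observed maximum change from baseline in Plasma HIV-1 RNA will be used as the response variable in the Emax model". Under SAP 11.1.1, Pearson correlations between change to Day 8 and "plasma GSK3640254 PK parameters will be summarized by treatment and overall".

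The Part 1 schedule (Protocol 2.2) puts Visit 5 on one of Days 8, 9 and 10; the other two days are virtual. RNA is drawn only at clinic visits. When Visit 5 is on Day 8 or 9, the return on the following day is for a PK draw alone (Protocol 9.5, Table 4, footnote 2). Part 2 schedules RNA on both Day 7 and Day 8 for everyone.

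The window table in SAP 13.3.1 groups Part 1 Days 8 to 10 as Visit 5, under the statement that "Analyses will be presented by scheduled visits as collected in the CRF". The only RNA derivation rule, in SAP 13.6.3, is "If there are two values within a time window, the latest value will be used for summaries and analyses".

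**The concern.** The cut is meant to give both parts the same number of doses behind the response. For a Part 1 participant with Visit 5 on Day 9 or 10 (called late below) it does not. The Visit 5 value is removed and nothing replaces it, so the last usable RNA is Visit 4. The exposure-response model still pairs that shortened response with Visit 5 PK from Day 9 or 10 (SAP 11.1.3).

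No rule says what to do. The duplicate-value rule does not apply, the missing-data section (SAP 13.7.2) has no efficacy imputation, and the window table cannot supply a Day 9 or 10 value that SAP 11.1.2 excludes. The per-protocol criteria (SAP 13.1.1) require a Visit 6 RNA, not a Day-8 one, so these participants stay in the model sets.

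The affected active arms, 10 mg and 200 mg, are the two ends of the fitted dose range. The relation of exposure to RNA change is a listed secondary objective (Protocol 4), and the study is meant to inform Phase 2b doses (Protocol 3.1).

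**Working it through.** The plan gives no figure to reproduce.

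**1. Which schedules lack a Day-8 RNA.** Visit 3 is on Day 3 or 4, Visit 4 on Day 5, 6 or 7, and Visit 5 on Day 8, 9 or 10. Footnote 2 of the Part 1 schedule limits the interval between visits to 3 days, read here as a difference in day number. Of 2 × 3 × 3 = 18 combinations, 9 are permitted:

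| Visit 5 | Permitted (Visit 3, Visit 4) | Last RNA by Day 8 |
|---|---|---|
| Day 8 | (3,5) (3,6) (4,5) (4,6) (4,7) | Day 8 |
| Day 9 | (3,6) (4,6) (4,7) | Day 6 or 7 |
| Day 10 | (4,7) | Day 7 |

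So 4 of 9 are late. A pre-dose sample on day d follows d − 1 doses: 5 or 6 for late participants, 7 on Day 8. All 4 Part 2 schedules include Day 8.

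**2. Assumptions for size.** Emax 1.7 log10 and ED50 11 mg are assumed. SD 0.4 is from Protocol 10.1.1. There are 6 participants per active arm (SAP 2.3). Mean response is Emax × D/(D + ED50), giving 0.81, 1.33, 1.50, 1.58 and 1.61 log10 at 10, 40, 80, 140 and 200 mg.

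**3. Change to Day 8 (late records missing).** With k late in each Part 1 arm, 30 − 2k active records remain. The gradient is g(D) = [D/(D + ED50), −Emax × D/(D + ED50)²], the information is Σ n g gᵀ/SD², and the SEs are the square roots of the diagonal of its inverse.

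| Late per Part 1 arm | 0 | 1 | 2 | 3 | 4 | 6 |
|---|---|---|---|---|---|---|
| SE(ED50), mg | 4.83 | 5.21 | 5.69 | 6.35 | 7.30 | 12.3 |

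With 3 late, SE(Emax) rises from 0.134 to 0.162, and each Part 1 arm's correlation rests on 3 pairs instead of 6.

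**4. Maximum change to Day 8 (window shortened).** Let f(d) be the share of the Day-8 decline reached by day d. The arm mean is understated by (late/6) × mean × (1 − f(Visit 4 day)). For 200 mg with 3 late:

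- Linear, f = (d − 1)/7: 0.5 × 1.61 × 1/7 = 0.12 for Visit 4 on Day 7; 0.5 × 1.61 × 2/7 = 0.23 for Day 6.
- Lag of L days, f = (d − 1 − L)/(7 − L): 0.13 and 0.27 for 1 day; 0.16 and 0.32 for 2 days.
- Flattening at rate r per day, f = (1 − e^(−r(d−1)))/(1 − e^(−7r)): 0.04 and 0.09 for r = 0.3; between 0.004 and 0.04 for r = 0.5 to 0.8.

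I refitted the Emax model to the shortened means, with Visit 4 on Day 6. All 30 records remain, so the reference SEs are 0.134 for Emax and 4.83 mg for ED50. With 3 late, Emax falls by 0.07 (linear), 0.085 (1-day lag) or 0.10 (2-day lag), and ED50 rises by 0.4 to 0.6 mg. With 4 late and a 2-day lag, Emax falls by 0.137; with all 6 late and linear decline, by 0.147. Both exceed one SE.

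**5. Candidate repairs for maximum change (200 mg, 3 late; error in log10).**

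| Decline | Observed only | Interpolated Day 8 | Visit 5 taken as Day 8 |
|---|---|---|---|
| Linear | −0.12 to −0.23 | 0 | +0.12 (Day 9) to +0.23 (Day 10) |
| Flattening, 0.3 to 0.8/day | −0.004 to −0.09 | −0.001 to −0.011 | +0.002 to +0.05 |
| Linear, stopping at Day 8 | −0.12 to −0.23 | −0.06 to −0.08 | 0 |

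**The case against.** Visit days are planned in advance around weekends, work and clinic hours (footnote 2 of the Part 1 schedule), so a missing Day-8 value is plausibly unrelated to response. The fitting procedure simply drops it. For change to Day 8 the plan as written is therefore an available-case analysis with a precision cost and no expected bias; interpolating there would replace it with a model-dependent one. This stands, and it limits the fix.

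Interpolation uses the Day 9 or 10 RNA that SAP 11.1.2 excludes, and puts a derived value into a response the SAP defines as observed. The rule would also be written after the sponsor had seen the unblinded Part 1 results (SAP 3.1). These are real costs, and the reason to show both versions.

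The SAP is not wholly silent. It allows model adjustments based on the data, and SAP 13.7.2 has participants excluded from analyses documented in the study report. Neither supplies a Day-8 value or restores the shortened window.

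The number affected is unknown. Protocol 3.2.4 dates the genotyped Visit 5 samples to Day 8 or 9, which suggests that Day 9 visits occurred but does not show in which arm or how many. The 3 of 6 used above is only an illustration.

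**Conclusion.** The point holds as a low-priority improvement. As written, the cut misses its own aim for late Part 1 participants: their maximum change reflects 5 or 6 doses, and their change to Day 8 is absent. On the stated assumptions with 3 of 6 late, the 200 mg mean maximum change is understated by 0.12 to 0.23 log10 under linear decline, up to 0.32 with a 2-day lag, and only 0.004 to 0.09 if decline flattens. There is no understatement if nobody was late or the nadir came by Visit 4. Emax moves by up to 0.10 against an SE of 0.13; with 4 or more late per arm the shift can exceed one SE. SE(ED50) for change to Day 8 goes from 4.8 to 6.4 mg, and to 12.3 mg if all 6 per arm are late.

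A reader might infer more than the documents support:

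- **That the primary result is biased.** It is not affected: the primary analyses are fitted by part, descriptive maximum change uses all visits, and no hypothesis is tested (SAP 2.4).
- **That change to Day 8 is biased.** Scheduling-driven visit days give no reason to expect that.
- **That about 4 in 9 participants were late.** Counting permitted schedules does not show how often each was used.
- **That the Day-8 cut should go.** Its aim of matching dosing days is reasonable.

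**What to change.** Keep the Day-8 cut and add to SAP 10.1.4 and 11.1.2:

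- **Maximum change to Day 8.** For a Part 1 participant whose Visit 5 RNA is after Day 8, interpolate the Day-8 log10 value linearly between Visit 4 and Visit 5. Use it as one further candidate for the maximum, and report the observed-only result alongside. Both samples are on treatment, because the models use the per-protocol or PK/PD set and SAP 13.1.1 excludes a "Participant who have missed at least one dose of GSK3640254".
- **Change to Day 8.** State that the available-case fit is the main analysis, with the interpolated value as a sensitivity analysis.
- **Visit 5 taken as Day 8.** Do not use it, or label it an upper bound.
- **Reporting.** Give the number affected per arm.

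The cost is a few lines of SAP text and at most 12 derived active-arm records. Interpolation is exact only for linear or lagged-linear decline. In the other shapes tried it reduced the error without removing it. It brings excluded Day 9 or 10 RNA back into a response defined as observed, under a rule written with Part 1 results known, so neither version should be reported without the other.
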